#### *Assessing tibial perfusion in response to leg dependency and reactive hyperemia (able-bodied and volunteers with SCI)*

We will use leg dependency and reactive hyperemia to assess myogenic vasoconstriction and myogenic vasodilation, respectively. This approach will provide insight to the relation between popliteal artery structure and myogenic vasoconstrictor response (leg dependency) and myogenic vasodilator response (reactive hyperemia), respectively.

Leg dependency (i.e. the limb is lowered below heart level such that the knee is flexed at 90deg) results in an increased arterial transmural pressure, thereby engaging myogenic vasoconstriction. [6] Past work showed that those with SCI have more pronounced decreases in blood flow during leg dependency compared to able-bodied. [7] Thus, myogenic vasoconstrictor responses might be enhanced in the paralyzed legs. In addition, reactive hyperemia (i.e. increased calf blood flow in response to sustained ischemia via proximal thigh cuff inflation) is significantly lesser in SCI compared to able-bodied. [7]–[9] Thus, the myogenic vasodilatory capacity of the arterieres in the legs of those with SCI might be impaired.

Throughout this aim, we will monitor continuously calf blood flow and tibial bone perfusion in the same leg. With the subject in supine position, we will obtain a 5 minutes resting baseline, followed by 5 minutes with the limb lowered below heart level (knee flexed at 90 deg). After 10 minutes of recovery, we will use reactive hyperemia to increase blood flow to the leg. With the subject supine, a pressure cuff placed above the knee will be inflated to supersystolic values (>200 mmHg) for 10 minutes. Data will be obtained for a 5 minutes resting baseline, 10 minutes during cuff inflation, and 5 minutes after cuff release.

## PARTNERS HUMAN RESEARCH COMMITTEE

### DETAILED PROTOCOL

#### *Assessing tibial perfusion in response to exogenous nitric-oxide (NO) (able-bodied)*

We will use an exogenous NO donor to assess NO-mediated vasodilation in the tibial bone vasculature of able-bodied. We will use one tablet of sublingual nitroglycerine (Nitroglycerine 0.4mg Sublingual table) as the NO donor. With the subject in supine position, we will obtain a 5 minutes resting baseline, followed by one tablet dissolved under the tongue, for 15 minutes. Throughout, we will continuously monitor heart rate and blood pressure, and calf blood flow and tibial bone perfusion in the same leg.

#### *Assessing tibial perfusion in response to increasing loading conditions (able-bodied and individuals with SCI with time since injury between 3 and 24 months)*

This approach will define the relationship between popliteal artery structure and magnitude of bone perfusion during loading of different magnitudes.

We will use a custom tibial loading device (see Measurements below) to provide three periods of static bone loading, in random order: 1) 10% of body weight, 2) 30% of body weight, 3) 50% of body weight.

After 10 minutes of recovery, the volunteers will undergo the three periods of cycling bone loading described below. The subjects will be seated with the leg secured in the boot of the tibial bone loading device. The knee will be maintained at 90 deg flexion. Bone loading will be applied across the tibia at the 3 magnitudes of loading. Tibial bone perfusion of the same leg will be monitored continuously. Each period of static loading will consist of a 5 minutes resting baseline, 10 minutes of loading, and 5 minutes of recovery.

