### II. SPECIFIC AIMS

- 1) Determine if popliteal artery structural changes are reflected in altered myogenic control of tibial bone perfusion post SCI.

*Hypothesis: Compared to able-bodied, those with SCI will demonstrate greater popliteal artery wall thickness and smaller diameter that will relate to both greater myogenic vasoconstriction (in response to leg dependency) and lesser myogenic vasodilation (in response to reactive hyperemia) in tibial bone.*

- 2) Determine if popliteal artery structural changes are reflected in lesser increases in tibial bone perfusion during compressive loading post SCI.

*Hypothesis: Compared to able-bodied, those with SCI will demonstrate greater popliteal artery wall thickness and smaller diameter that will relate to smaller increases in bone perfusion with increasing loading conditions.*

- 3) Determine if nitric-oxide mediated vasodilation is present in the tibial bone vasculature of able-bodied.

*Hypothesis: In able-bodied, the tibial bone vasculature vasodilates in response to a nitric oxide donor.*

All able-bodied volunteers will complete both aim1 and aim2. Only a subset of volunteers with SCI – those with time since injury between 3 and 24 months post injury – will be included for aim 2. The proposed study will investigate the control of bone perfusion in the SCI population as it relates to vascular remodeling and loading conditions.

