### III. SUBJECT SELECTION

#### **Inclusion criteria**

We anticipate we will recruit 29 individuals (males and females) aged 18 to 40 years with injuries, American Spinal Injury Association Impairment Scale (AIS) A and B and C. For aim 2, only individuals with SCI with complete injuries between 3 and 24 months post injury will be included. In addition, we will recruit 29 healthy individuals (males and females) age and gender matched to enroll for this study.

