#### Statistics

Data from NIRS monitoring will be used to determine hemoglobin content changes in tibial bone from changes in light absorption on a moment-by-moment basis. A detailed description of the analysis can be found in our previous work. [12] Briefly, NIRS monitoring provides a change in hemoglobin content from one state to another. This is due to the fact that absolute intensity of the scattered light measured across the tibia cannot be used for an absolute measure of perfusion. However, as perfusion increases, there is a proportional increase in absorption (and vice versa). Thus, percent change in total hemoglobin detected reflects the relative change in perfusion.

The main outcomes assessed will be popliteal artery thickness and lumen diameter, tibial perfusion, and whole leg blood flow. This project will employ a simple and straightforward statistical approach to compare responses within and between groups. Statistical significance will be set at 0.05, and power at 80%. Descriptive statistics will be presented including mean, median, standard deviation, and range. Differences/relations will be considered as statistically significant at alpha=0.05 level. For all parametric statistical tests, conformity of data to required statistical assumptions will be verified using standard methods. If assumptions for parametric tests do not hold, non-parametric alternatives will be employed. The analysis plan is written as though there are no distributional problems; assumptions for all analyses will be checked and analogous methods calling for fewer and/or weaker assumptions will be used, if called for. For the data from aim 1, unpaired t-tests will be used to assess changes in perfusion between groups and reactive

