## PARTNERS HUMAN RESEARCH COMMITTEE

### DETAILED PROTOCOL

hyperemia/leg dependency. Since the two conditions result in distinct and opposite responses, they should be considered separately. For the data from aim 2, for the three passive loading conditions (10%, 30%, 50% body weight without associated muscle contractions), a 2x3 ANOVA will be used to assess changes in perfusion between groups across loading conditions.

The results of this study will provide invaluable insights into bone perfusion in the paralyzed legs of those with SCI. For both aims, we anticipate that individuals with SCI will have less bone perfusion compared to able-bodied due to the extensive vascular maladaptations. Even if the results are not different between those with SCI and able-bodied, this study will have explored a potentially key contributor to SCI-related bone loss, with major implications in treating osteoporosis.

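### Aim 2 load order is random with no balancing described and no period term in the model, which costs avoidable precision in the load-specific and group-by-load comparisons

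*Combined protocol and SAP*

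**What the plan says.** The combined document holds two protocols; this point concerns the first, on vascular structure and tibial loading after SCI.

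- **Order.** Section V, in the part on increasing loading conditions, uses the device "to provide three periods of static bone loading, in random order". It does not say how the order is generated or whether it is balanced, overall or within group.
- **Timing.** "Each period of static loading will consist of a 5 minutes resting baseline, 10 minutes of loading, and 5 minutes of recovery". If periods follow each other directly, consecutive loads are separated by 5 + 5 = 10 unloaded minutes.
- **Who is loaded.** Section II: "All able-bodied volunteers will complete both aim1 and aim2", but "Only a subset of volunteers with SCI" enter Aim 2. Section III narrows this: "For aim 2, only individuals with SCI with complete injuries between 3 and 24 months post injury will be included". The size of the subset is not given. Section III plans "29 healthy individuals (males and females) age and gender matched to enroll for this study".
- **Outcome.** Section VI, Statistics: "percent change in total hemoglobin detected reflects the relative change in perfusion".
- **Analysis.** Section VI, Statistics: "a 2x3 ANOVA will be used to assess changes in perfusion between groups across loading conditions". No period, sequence or carry-over term is mentioned.

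**The concern.** Three loads can be given in six orders. If each volunteer's order is drawn independently, the mix of orders will differ by chance between the able-bodied and SCI groups, and the more so the smaller the SCI subset. Volunteers sit with the knee at 90 degrees through three 20-minute periods, so some drift in the perfusion signal over the hour is plausible. Where drift exists, a load given earlier on average in one group than in the other picks up a different share of it.

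The Aim 2 hypothesis is that perfusion rises less with increasing load in SCI. That is a statement about the group-by-load pattern, which is where unequal order acts. The planned ANOVA has nothing to take drift out of either the load means or the residual.

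**Working it through.** The documents give no figure on order allocation to reproduce. The inputs are 29 able-bodied volunteers (Section III), an SCI subset of unstated size (8 to 29 assumed), and three loads in six orders. Drift size is an assumption, in units of the residual SD within person.

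**1. How unequal can order be?** With independent random orders, the number given 50% first is Binomial(n, 1/3) in each group. The SD of the difference in shares is √[(1/3)(2/3)(1/n_SCI + 1/29)]. For n_SCI = 12 this is √(0.2222 × 0.1178) = 0.162.

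| SCI loaded | SD of difference | P(difference ≥ 20 points) |
|---|---|---|
| 8 | 0.188 | 28.5% |
| 12 | 0.162 | 21.4% |
| 17 | 0.144 | 16.8% |
| 29 | 0.124 | 12.5% |

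**2. Where does a common drift go?** Let the response change by 1 unit per period, and let one group have a 20-point excess of 50%-first orders. The 50% load's mean position falls by 0.20 × 1.5 = 0.30. The three positions always sum to the same total, so the other two loads each move by +0.15. The shifts at 10%, 30% and 50% are +0.15, +0.15 and −0.30. Their mean is zero, so nothing reaches the overall group difference. The 50%-minus-10% contrast moves by −0.30 − 0.15 = −0.45.

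**3. What does this cost in precision?** The position of 50% minus the position of 10% is ±1 with probability 1/3 each and ±2 with probability 1/6 each, so its variance is (2/3)(1) + (1/3)(4) = 2. With residual SD 1 and drift δ per period, one person's 50%-minus-10% contrast has variance 2 + 2δ². The SD of the group difference in that contrast is therefore √[2(1 + δ²)(1/n_SCI + 1/29)]. For 12 SCI volunteers:

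- δ = 0: √(2 × 0.1178) = 0.49
- δ = 0.5: √(2.5 × 0.1178) = 0.54
- δ = 1: √(4 × 0.1178) = 0.69

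Simulation of the 2x3 ANOVA with unrestricted orders agrees (0.487, 0.542 and 0.687). With orders in permuted blocks of six within each group, the SD is 0.49 at both drift levels. The share of variance removed is δ²/(1 + δ²): 20% at δ = 0.5 and 50% at δ = 1. The SD of the overall group difference stays at 0.39 to 0.40 either way.

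**4. Is there bias or excess type I error?** Over repeated randomisation the mean error was about zero, and type I error was about 0.05 for the overall, 50%-load and interaction tests in every unbalanced setting. Drift under random order behaves as extra residual noise, and the ANOVA's error term includes it.

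**5. Is balance enough without a period term?** No. Balance takes drift out of the load means, but drift stays in the residual, so the error term is too large. With 12 SCI volunteers, the interaction test's type I error falls to 0.024 at δ = 0.5 and 0.003 at δ = 1. The precision gained would not reach the test.

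**The case against.** Randomising order is itself the safeguard, and it works as intended: no systematic bias and a valid test. That stands. A reader might infer that unequal order invalidates the SCI versus able-bodied comparison. The documents do not support that: every loaded participant is to receive all three loads, so a common drift cancels from the overall difference, and what remains is chance noise in load-specific and group-by-load estimates.

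A reader might also take it as established that orders are unbalanced and that the SCI subset is small. Both would be read from silence: the protocol may intend a balanced list, and it does not state the subset size.

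Carry-over invites a further stronger reading: that a raised baseline after the 50% load depresses the next response, and does so differently in SCI. The protocol provides a recovery and a fresh baseline in each period and gives no data showing that perfusion is still raised after them. Its evidence of smaller hyperaemic responses in SCI concerns release of a thigh cuff, not static tibial loading. If carry-over did differ by group, balancing would not cure it: over the six orders, the 10% and 30% loads each directly follow the 50% load in one third of sequences in both groups, so the unequal effect stays in the group means. It needs a separate check.

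Nor do the documents establish one-to-one pairs whose members could share an order. Age and gender matching may be at group level, and the Aim 1 tests are unpaired.

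**Conclusion.** The point holds as a cheap improvement in precision, not as a defect in validity. The order-generation method is unstated and the model has no period term. If responses drift, the 50%-minus-10% group contrast is noisier than it need be: with 12 SCI volunteers against 29 controls, an SD of about 0.54 rather than 0.49 at 0.5 residual SD of drift per period, and about 0.69 rather than 0.49 at 1 SD. With no drift there is nothing to gain and almost nothing to lose.

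These sizes rest on assumptions that the documents cannot confirm: the SCI subset size, a linear drift common to both groups, its magnitude, and independent random orders. A drift that differs by group would not cancel from the overall group difference, whatever the orders.

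**What to change.** 1. In Section V, state how order is generated. Allocate the six orders in balanced blocks, separately within the SCI loading group and the able-bodied group.
2. In Section VI, add period (1st, 2nd, 3rd) as a within-subject factor to the Aim 2 model. It must accompany balanced orders, because balance alone makes the interaction test conservative. It also adjusts for imbalance left by an incomplete last block: 8 SCI volunteers, for example, leave two outside a full block of six.
3. As a sensitivity analysis, re-express all three responses against the single baseline before the first load. Perfusion is to be recorded continuously in the same leg, so no new measurement is needed. A material change from the main analysis would point to carry-over, which balancing does not remove if it differs by group.

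The cost is a prepared order list and two degrees of freedom, with negligible loss of precision if there is no drift. Loads, visit length and sample size are unchanged.

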#### **Measurements**

[figure not shown]
[figure not shown]
*Tibial Blood Flow.* A custom made bone optical spectropscopy device that uses near-infrared (NIR) light will be used to continuously monitor tibial perfusion. Near infrared spectroscopy (NIRS) provides a safe, non-invasive, and inexpensive alternative to analyze hemodynamic changes in the biological tissues using light in the range of 600 to 1000 nm. The system has been previously used in Protocol #2014P002003 without any side effects. The system has two detectors allowing estimation of hemoglobin changes in a two layer (skin and bone) model and uses a broadband light source and high-sensitivity spectrometers to yield full NIR spectral information. The instrument uses a white-light tungsten halogen lamp (Fostec DCRII, Dallas, TX) to deliver light through a large optical fiber bundle to the skin. Two detector fibers are coupled with spectrometers (Mini-spectrometer TG C9405CB, Hamamatsu Photonics, Japan), placed at 1 and 2 cm distances from the source. Both spectrometers allow measurement of the diffusely reflected light between 650 nm and 800 nm with 5 nm resolution. The light source and the two detectors are attached to a custom made probe head placed on the skin surface directly over the tibia. Light propagates between the source and the detectors in "banana-shaped" sensitivity functions and penetrates shallower for more closely separated source-detector pairs and more deeply for wider separated pairs. Thus, the detector 1 cm from the source probes the relatively thin (2 mm) skin layer, whereas the detector 2 cm from the source probes deeper into tissue and is therefore sensitive to the underlying bone. Placing the probe on the anterior side of the middle third tibia where the bone lies directly under the skin minimizes the effects of soft tissue and local changes in skin

# PARTNERS HUMAN RESEARCH COMMITTEE

## DETAILED PROTOCOL

blood flow on the NIRS measurements. The extended modified Beer-Lambert law for a two-layer model will be used to determine hemoglobin content changes in tibial bone from changes in light absorption.

*Tibial Loading Device.* The custom-made device allows for controlled, compressive loading of the bone. The system consists of a boot with 2 inch strap over the knee. Wires pull vertically down on the brace via a cam-type device on a motor (Lesson, 90V DC). The load is monitored by air pressure cylinders on either side of the boot and the peak load cannot exceed the pressure of the cylinders. The servo-controlled pressure adjusts the load such that it remains at the predetermined level. This allows for full control of the magnitude and pattern of loading on the lower leg. This system can apply static or cycling loading on the tibia. This approach has been modeled after a mouse tibial loading model that has been successfully employed to examine bone adaptations under imposed physical loading conditions. The system is able-to non-invasively apply loading in a physiological direction and axially loads a single skeletal element – the tibia. The system also allows for isometric muscle contractions in the calf (plantar flexion) that can be performed in synchrony with the compressive loading and provides a stimulus that more closely mimics walking. The leg of the volunteer is placed in the boot of the device and secured with the strap over the knee. This ensures that the knee is maintained at 90 deg flexion throughout loading. Bone loading will be applied axially along the tibia and maintained constant at the different loading magnitudes. The loading force will be monitored and recorded via the two load cells place on either sides of the boot

# PARTNERS HUMAN RESEARCH COMMITTEE

## DETAILED PROTOCOL

*Beat-by-Beat Calf Blood Flow.* We will use Doppler derived flow velocities to estimate whole limb blood flow through the popliteal artery. A continuous wave 4 MHZ Doppler probe (Multidop T2, DWL) is placed against the skin under the knee to isolate the popliteal artery proximal to the bifurcation.

*Popliteal Artery Structure.* A linear 6- to 15- MHz Doppler ultrasound (SonoSite Edge II, Fujifilm SonoSite, Bothell, WA) will be used to measure popliteal artery thickness and lumen diameter. The measurements will be taken at the distal popliteal artery above 2cm above arterial take-off, with the subject in supine position with the knee flexed at 45deg. The arterial diameter will be measured on transverse images, with the ultrasound beam perpendicular to the artery. [18]

*Tibial Length.* Tibial length will be measured in sitting position with a tape measure.

*Body Weight.* Weight will be measured on a scale.

### VI. STATISTICAL ANALYSIS

#### Sample Size

Our prior work found a borderline significant increase ( $p=0.06$ ) in tibial perfusion after exercise in able-bodied. Power analysis at 80% of these data showed that 17 subjects would have provided a  $p<0.05$  increase in perfusion. Therefore, for this study, we based our sample size on this calculation. We do not expect any sex-related difference; moreover, the SCI population is comprised primarily of males. To ensure a sufficient sample size for NO-mediated vasodilation, we will aim to recruit an additional of 17 individuals in each group. Therefore, we will recruit 29 individuals with SCI (men and women) and 29 healthy individuals (men and women) to participate in the study.

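### The first protocol's 29 per group does not follow from its stated inputs (17 + 17 = 34), and 80% power is not shown for the SCI versus able-bodied tests

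*Combined protocol and SAP*

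**What the plan says.** The combined document holds two protocols. This point concerns the first, which has the nitric-oxide aim.

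- **Base figure.** Section VI, Sample Size, cites earlier work in which tibial perfusion rose after exercise in able-bodied people (p = 0.06). It continues: "Power analysis at 80% of these data showed that 17 subjects would have provided a" significant increase. The section adopts this as the basis for the study.
- **Increment.** "To ensure a sufficient sample size for NO-mediated vasodilation, we will aim to recruit an additional of 17 individuals in each group".
- **Total.** It then concludes: "we will recruit 29 individuals with SCI (men and women) and 29 healthy individuals (men and women"). Section III, Inclusion criteria, repeats the SCI figure ("We anticipate we will recruit 29 individuals (males and females) aged 18 to 40 years with injuries") and gives 29 matched healthy individuals.
- **Who takes nitroglycerin.** The Aim 3 hypothesis in section II reads "In able-bodied, the tibial bone vasculature vasodilates in response to a nitric oxide donor". The procedure in section V agrees: "We will use an exogenous NO donor to assess NO-mediated vasodilation in the tibial bone vasculature of able-bodied".
- **Tests.** Section VI, Statistics, says "Statistical significance will be set at 0.05, and power at 80" per cent. It names unpaired t-tests between groups for Aim 1 and a 2x3 ANOVA (group by load) for Aim 2.
- **Aim 2 SCI group.** "For aim 2, only individuals with SCI with complete injuries between 3 and 24 months post injury will be included". The number expected to qualify is not given.

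**The concern.** The enrolment target is presented as the result of a derivation that does not produce it. A reader cannot tell whether the base, the increment or the total is wrong, or why people with SCI receive an increment meant for a test they do not take.

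The only power calculation also concerns a different kind of test from those planned for Aims 1 and 2. A change within one group and a difference between two groups have different variances and different effects of interest, so 80% for the first says nothing direct about the second.

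This affects how the results are read. The Statistics section already plans how to interpret a finding of no difference between SCI and able-bodied. Without a stated detectable difference, such a finding cannot be told apart from a lack of power.

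**Working it through.** **1. The sum.** Inputs from the Sample Size section: base 17, increment 17 in each group, total 29 per group.

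- 17 + 17 = 34 per group, so 2 × 34 = 68. The plan has 29 per group, 2 × 29 = 58, which is 5 fewer per group.
- If the increment went only to the group that takes nitroglycerin: 34 able-bodied and 17 SCI, 51 in total. This is not 29 and 29 either.
- Dropout inflation of 17 as n/(1 − dropout) gives 19, 20, 22 and 25 at 10%, 15%, 20% and 30%. It reaches 29 only near 40%, and this protocol states no dropout rate. Inflation cannot bring 34 down to 29.

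**2. What the 17 implies.** The earlier study's size, mean change and SD are not given, so its power calculation cannot be repeated. Working back with a one-sample (paired) t-test, noncentral t, two-sided 0.05 (sidedness is my assumption):

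- 80% power at n = 17 implies a standardised change d = 0.724.
- If 17 was rounded up, d could be as high as 0.749, the value for n = 16.

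**3. Aim 1, without assuming an effect.** Smallest difference detectable by an unpaired t-test at 80% power, two-sided 0.05:

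| Able-bodied / SCI | Detectable difference |
|---|---|
| 29 / 29 | 0.75 SD |
| 34 / 34 | 0.69 SD |
| 34 / 17 | 0.85 SD |

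**4. Aim 1, conditional illustration.** Assume the post-exercise effect and SD carry over to the group comparison. Power at 29 versus 29:

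- difference equal to the whole change (d = 0.724): 77%; at d = 0.749, 80%
- three quarters of it (0.75 × 0.724 = 0.543): 53%
- half of it (0.5 × 0.724 = 0.362): 27%

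The fractions are illustrative and come from no passage. They do not apply to leg dependency, where a greater response is expected in SCI.

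**5. Aim 2, group effect of the ANOVA.** Assume 29 able-bodied, an SCI subset of 10, 15 or 20, the same group difference at each load, and within-person correlation rho between loads. The group effect is then a t-test on each person's mean of three loads, whose SD is sqrt((1 + 2·rho)/3) times the SD at one load. Detectable difference per load at 80% power:

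| rho | 10 SCI | 15 SCI | 20 SCI |
|---|---|---|---|
| 0.5 | 0.86 SD | 0.74 SD | 0.68 SD |
| 0.7 | 0.94 SD | 0.82 SD | 0.74 SD |
| 1 (as a single measure) | 1.06 SD | 0.91 SD | 0.83 SD |

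Example: 29 versus 15 detects 0.912 SD on a single measure. With rho = 0.5, sqrt(2/3) = 0.816, and 0.912 × 0.816 = 0.74.

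**6. Aim 3.** For a one-group paired test, if the exercise effect (d = 0.724) applies to nitroglycerin, power is 80% at n = 17 and 96% at n = 29.

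**The case against.** **The 34 is one reading.** The text does not say expressly what the extra 17 are added to, and 12 + 17 = 29 would fit. But no 12 appears in this protocol, and the sentence just before adopts the 17 as the basis. It stands that 34 is what the wording implies, not a proven correct total.

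**The 80% may be only a convention.** It stands beside alpha in a plan for comparisons both within and between groups, and the Sample Size section ties it to the exercise data. That supports the within-group test of Aim 3. It leaves Aims 1 and 2 with no power basis at all.

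**Power may be close to nominal.** If the one-group effect carries over whole, power is 77% to 80% at 29 per group. A one-sided reading gives d = 0.63 and again 77%. This stands, and it is why the finding is that power is not shown, rather than that it is low.

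**Matching could explain equal groups.** The healthy group is matched on age and gender. However, the plan gives nitric oxide, not matching, as the reason for the increment.

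**Aim 2 may turn on the interaction.** Its hypothesis, smaller increases with increasing load, can be read as group by load. The group effect in step 5 is then only part of the answer. For 29 versus 15, the group difference in the change from 10% to 50% load has SD sqrt(2(1 − rho)) times the single-load SD. It is detectable at 0.91 SD for rho = 0.5 and 0.71 SD for rho = 0.7, so higher correlation helps here and hurts the group effect. This stands, and the fix includes it.

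**The target itself is clear.** Both sections say 29 and 29. True, but its justification contradicts it.

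**Conclusion.** The concern holds and must be fixed. The stated inputs give 34 per group, 5 more than the 29 planned, and no stated step closes the gap. The reason for the increment applies to able-bodied volunteers only. These two points rest on the text alone.

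For Aims 1 and 2, 80% power is not shown, because the 17 comes from a one-group change and no between-group difference or SD is given. The figure least dependent on assumptions is 0.75 SD detectable at 29 versus 29 (80% power, two-sided 0.05). The powers of 77%, 53% and 27% depend on carrying over the exercise effect. The Aim 2 range of 0.68 to 1.06 SD depends on assumed subset sizes and correlations. The documents do not establish that the study is underpowered, nor which of 17, 17 and 29 is the mistaken figure.

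**What to change.** Rewrite the Sample Size paragraph:

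1. Reconcile 17 + 17 with 29, and state the inputs and total for each group. Make Inclusion criteria agree.
2. Stop attributing the nitric-oxide increment to the SCI group. Give Aim 3 its own able-bodied n, as a one-group paired test.
3. Limit the 80% statement to that one-group test, and state whether tests are one- or two-sided. For Aim 1, give the expected between-group difference and SD, or the detectable difference at the final n (0.75 SD if 29 versus 29).
4. For Aim 2, state the expected size of the SCI subset and the assumed within-person correlation. Report the detectable difference for the group effect and, beside it, for the group-by-load contrast.

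The cost is one reworded paragraph, one between-group assumption (or a detectable difference) and one expected subset size. With recruitment kept at 29 and 29, no participants are added, and the 80% claim becomes narrower. If the sponsor finds that 34 was intended, raising the target by 5 per group is a separate decision that this correction does not require.
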